# 11. Safety Analyses

Unless otherwise specified, all the safety analyses will be based on the Safety population as defined in Section 6 and summaries will include all events or assessments collected during the study.

All safety data will be reported by cohort. Safety analyses will include but not limited to summaries of AEs, laboratory measures, and vitals. AEs will be summarized by maximum toxicity grade for each cohort. The toxicity grade for laboratory data will be calculated using NCI CTCAE v4.0 The lab data will then be summarized according to the subjects' baseline grade and maximum grade for each cycle of therapy.

# 11.1. Extent of Exposure

The duration of exposure to Pazopanib in days (from first day to last day of treatment) will be summarised by cohort. Descriptive statistics including mean, median, standard deviation, minimum, and maximum will be calculated for time on study treatment. Exposure categories (in weeks) will also be summarized.

Average daily dose will be calculated as Cumulative dose (mg) / Duration of exposure to study treatment (day), and summarized by cohort, using the mean, standard deviation, median, minimum, and maximum. Actual duration of exposure will be calculated as the date of last dosing-date of first dosing+1.

Study drug dose received will be summarized by cohort. Cumulative dose, actual dose intensity and relative dose intensity will be presented. Actual dose intensity will be calculated as actual total dose/actual duration of exposure. Relative dose intensity will be calculated as (actual dose intensity/planned dose intensity)\*100. Planned dose intensity will be calculated as planned total dose/planned duration of exposure, where planned duration of exposure will be the same as actual duration of exposure.

A by-subject listing of data on subject exposure including dose reduction, dose interruptions and the corresponding reasons will be produced.

The safety population will be used for all summaries and listing of study treatment.

# 11.2. Adverse Events

AE summaries will include all AEs occurring during on-therapy period. All AEs collected in the AE (e)CRF page will be listed along with the information collected on those AEs e.g. AE relationship to study drug, AE outcome etc. AEs with start date outside of on therapy period will be flagged in the listings.

An overview summary of AEs, including counts and percentages of subjects with any AE, grade /4 AEs, AEs related to study treatment, AEs leading to permanent discontinuation of study treatment, AE leading to dose reductions, AEs leading to dose interruptions, SAEs, SAEs related to study treatment, fatal SAEs, and fatal SAEs related to study treatment will be produced

A summary of on-therapy AEs will be provided by primary system organ class (SOC) and preferred term (PT) and by PT only All non-serious adverse events, regardless of study drug relationship, by SOC and PT will be summarized.

Adverse events (AEs) will be graded according to the CTCAE, Version 4.0. Adverse events will be coded to the preferred term (PT) level using the Medical Dictionary for Regulatory Affairs (MedDRA ).

In AE summaries, the frequency and percentage of AEs (all grades) will be summarized and displayed in two ways: 1) in descending order of total incidence by PT only and 2) in descending order of total incidence by System Organ Classes (SOC) and PT. In the SOC row, the number of subjects with multiple events under the same system organ class will be

counted once. The primary system organ class (SOC) will be presented alphabetically and the preferred terms will be sorted within primary SOC in descending frequency. The sort order for the preferred term will be based on their frequency.

In addition, a summary of number and percentage of subjects with any on-therapy adverse events by maximum grade will be produced. AEs will be sorted by preferred term (PT) in descending order of total incidence. The summary will use the following algorithms for counting the subject:

- **Preferred term row**: Subjects experiencing the same AE preferred term several times with different grades will only be counted once with the maximum grade.
- Any event row: Each subject with at least one adverse event will be counted only once at the maximum grade no matter how many events they have.

A separate summary will be provided for study treatment-related AEs. A study treatmentrelated AE is defined as an AE for which the investigator classifies the relationship to study treatment as "Yes". A worst case scenario approach will be taken to handle missing relatedness data, i.e. the summary table will include events with the relationship to study treatment as 'Yes' or missing. The summary table will be displayed in descending order of total incidence by SOC and PT and by PT only. Note all treatment-related AEs will be included in the summary regardless of assessment window.

All AEs will be listed.

A listing of adverse events recorded as dose-limiting toxicities will be provided. Additionally, a summary of the number of subjects experiencing DLT's in each cohort will be provided.

# 11.3. Identified and Potential Risks

N.A.

# 11.4. Deaths and Serious Adverse Events

In the event that a subject has withdrawn consent, no data after the withdrawal of consent date from this subject including death is supposed to appear in the database. Ensuring that this rule is followed should be part of the data cleaning process.

All deaths will be summarised based on the number and percentage of subjects. This summary will classify subject status (dead, alive at last contact follow-up ended, alive at last contact follow-up ongoing), subjects by time of death relative to the last dose of medication (>28 days or  $\leq$ 28 days), and primary cause of death. A supportive listing will be generated to provide subject-specific details on subjects who died.

All SAEs will be tabulated based on the number and percentage of subjects who experienced the event by cohort. Separate summaries will also be provided for study treatment-related SAEs, fatal SAEs and study treatment related fatal SAEs. Treatment-related SAE by SOC, PT, and maximum CTC grade will be summarized. The summary tables will be displayed in descending order of total incidence by SOC and PT and by PT only.

A study treatment-related SAE is defined as an SAE for which the investigator classifies the relationship to study treatment as "Yes". A worst case scenario approach will be taken to handle missing data, i.e. the summary table will include events with the relationship to study treatment as 'Yes' for missing.

SAEs are included in the listing of all adverse events. Separate supportive listings with subject-level details will be generated for

- Fatal SAEs
- Non-Fatal SAEs.

For the legal requirements of ClinicalTrials.gov and EudraCT, two required tables will be generated.

(1) On-therapy adverse events which are not serious adverse events with an incidence greater than 5%.

If for a same subject, several consecutive AEs (irrespective of study treatment causality, seriousness and severity) occurred with the same SOC and PT:

- a single occurrence will be counted if there is ≤ 1 day gap between the end date of the preceding AE and the start date of the consecutive AE
- more than one occurrence will be counted if there is > 1 day gap between the end date of the preceding AE and the start date of the consecutive AE

For occurrence, the presence of at least one SAE / SAE suspected to be related to study treatment / non SAE has to be checked in a block e.g., among AE's in a  $\leq 1$  day gap block, if at least one SAE is occurring, then one occurrence is calculated for that SAE

(2) On-therapy deaths and serious adverse event by system organ class and preferred term including the number of deaths resulting from SAEs suspected to be related to study treatment and SAEs irrespective of treatment.

#### 11.5. Adverse Events Leading to Discontinuation of Study Treatment and/or Withdrawal from the Study and Other Significant Adverse Events

The following categories of AEs will be summarized separately in descending order of total incidence by SOC and PT and separate supportive listings will be generated with subject level details for those subjects:

- AEs Leading to Discontinuation/Withdrawal of Study Treatment
- AEs Leading to Dose Interruptions
- AEs Leadings to Dose Reductions

# 11.6. Pregnancies

While pregnancy itself is not considered to be an AE or SAE, any pregnancy complication or elective termination of a pregnancy for medical reasons will be recorded as an AE or SAE as described in the protocol. If subjects become pregnant while on the study, the information will be included in the narratives and no separate table or listing will be produced.

# 11.7. Clinical Laboratory Evaluations

Data from all sources (central and local laboratories) will be combined. The summaries will include all laboratory assessments collected no later than 28 days after the last study treatment administration date. All laboratory assessments will be listed and those collected later than 28 days after the last study treatment date will be flagged in the listings.

Laboratory data will be classified into CTC grades according to the NCI CTCAE v4.0. For all reports, CTC grade is always obtained on the converted measurement in SI unit. Grade 5 will not be used. The CTC grade 0 will be assigned as below in different scenarios:

- 1. For lab parameters defined by criteria based on normal range only, a severity grade of 0 will be assigned when the value is within normal limits.
- 2. For lab parameters whose grade is defined by criteria based on normal range and absolute values (e.g. platelet count decrease). A severity grade of 0 will be assigned when the value is within normal limits.
- 3. For lab parameters whose grade is defined by criteria based on normal range and the change from baseline value, with no other associated clinical criteria such as concomitant medication (e.g. creatinine increased) the following will be applied. For the baseline grading and for the grading of post-baseline lab values with missing baseline grading, the grade will be derived using the criteria based only on the normal range as per CTCAE v4.0. A severity grade of 0 will be assigned when the post-baseline value is ≤ ULN (for hyper) or ≥ LLN (for hypo).

Parameters for which a grading does not exist will be classified into low/normal/high group by means of laboratory normal ranges.

CTC grading for blood differentials is based on absolute values. However, this data may not be reported as absolute counts but rather as percentage of WBC.

The following rules will be applied to derive the WBC differential counts when only percentages are available for a xxx differential

xxx count = (WBC count) \* (xxx %value / 100)

The following summaries will be produced by cohort for the hematology and Biochemistry laboratory data:

• Shift tables using CTCAE grades to compare baseline to the worst post-baseline value.

• For laboratory tests where CTCAE grades are not defined, shift tables using the low/normal/high/(low and high) classification to compare baseline to the worst post-baseline value.

The following listings will be produced for laboratory data:

- Listing of subjects with laboratory abnormalities of CTC grade 3 or 4
- Listing of subjects with laboratory values outside the laboratory normal ranges with values flagged to show the corresponding CTCAE grades and the classification relative to the laboratory normal range. Non- normal lab values collected outside the on-threapy period will be also reported in listings and flagged accordingly.

Summaries will include data from scheduled assessments only except for the worst case post baseline which will include all post baseline assessments including unscheduled visits, and all data will be reported according to the nominal visit date for which it was recorded; no visit windows will be applied.

Summary of lab values and change from baseline by scheduled visits using mean, median, standard deviation, minimum and maximum will be provided. Supporting listings of all laboratory data will be provided including scheduled and unscheduled assessments and values identified from SAE reports.

Unless otherwise specified, the denominator in percentage calculation at each scheduled visit will be based on the number of subjects with non-missing value at each particular visit.

### 11.7.1. Analyses of Liver Function Tests

Summaries of hepatobiliary laboratory events including possible Hy's law cases will be provided in addition to what has been described above. Liver function parameters of interest are total bilirubin (TBL), ALT, AST and alkaline phosphatase (ALP).

Possible Hy's law cases are defined as any elevated AST or ALT>3×ULN, total bilirubin $\geq 2\times$ ULN and ALP<3×ULN/missing. Total bilirubin $\geq 2\times$ ULN can be within 28 days following the ALT elevation and if direct bilirubin is available on the same day, it must be  $\geq$  35% of total bilirubin. ALP<3xULN/missing means the criteria is satisfied unless the ALP is  $\geq 3xULN$  at any time of bilirubin elevation within the 28 days window.

Following supporting listings will be provided:

- Listing of Potential Hy's Law Cases
- Listing of Liver Events in Relation to Time of Treatment

listing of laboratory data (virology) will be provided.

### 11.8. Other Safety Measures

Unless otherwise specified, the denominator in percentage calculation at each scheduled visit will be based on the number of subjects with non-missing value at each particular visit. **Vital Signs** 

Values of vital signs (blood pressure, heart rate, and temperature) and weight as well as the change from baseline collected on-therapy will be summarized by scheduled visit using mean, median, standard deviation, minimum and maximum. Values measured outside of on-therapy period will be flagged in the listing.

For analysis of vital signs, the clinically notable vital sign criteria are provided in Section 9.4.3. **Error! Reference source not found.** Vital signs shift table based on values classified as notable low, normal, notable high or notable (high and low) at baseline and worst post-baseline will be produced by cohort for systolic blood pressure, diastolic blood pressure, heart rate, and body temperature. Baseline is defined as the last non-missing value prior to or coinciding with first dose. The worst post-baseline value refers to the worst post-baseline value on therapy.

#### **Performance Status**

Lansky and Karnofsky performance status will be summarized at baseline and each postbaseline scheduled visit. Summaries will use frequency and percentage of subjects at each planned assessment time. A summary of change from baseline by scheduled visits will be performed, as well as the worst case post-baseline and the best case post-baseline changes during the study.

A supporting listing will also be provided.

#### ECG

A summary of the number and percentage of subjects who had normal and abnormal (clinically significant and not clinically significant) ECG findings will be displayed by scheduled visits as well as for the worst case post-baseline.

All ECG summaries will include assessments performed no later than 28 days after the last date of study drug. All ECG assessments will be listed, and those collected later than 28 days after study drug discontinuation will be flagged in the listing.

The number and percentage of subjects with clinically notable ECG values will be presented by cohort. The clinically notable ECG criteria are provided in Section 9.4.2.

For each of the QTc and QT intervals, shift tables based on notable parameter categories ( $<450, 450 - <480, 480 - <500, \ge 500$  ms) and normal range at baseline and the worst postbaseline value observed will be produced.

The changes in QTc values will be categorized into the clinical concern ranges which are specific to changes in QTc: 31-60 and >60 msec. A summary of change in QTc value will display the number and percentage of subjects with a change within each range at each scheduled assessment time and in the worst case post-baseline assessment. Subjects with missing baseline values will be excluded from this summary.

Unscheduled ECG measurements will be used in the analysis of notable ECG changes and the shift table analysis of notable QT parameters for the worst case post baseline assessment.

Listings of abnormal ECG findings and a listing of ECG values will be provided. **LVEF** 

Absolute change from baseline in LVEF will be summarized at each scheduled assessment time and in the worst case post-baseline. Only the post-baseline assessments that used the

same method (ECHO or MUGA) as the baseline assessments will be used to derive the change from baseline. The change from baseline will be categorized as follows:

- Any increase
- No change
- Any decrease:
  - 0 <10% Decrease
  - 10 <20% Decrease
  - $\circ \geq 20\%$  Decrease
- $\geq 10\%$  decrease and  $\geq LLN$
- $\geq 10\%$  decrease and < LLN
- $\geq 20\%$  decrease and  $\geq LLN$
- $\geq 20\%$  decrease and < LLN

LVEF results will also be listed with subject level details including absolute change from baseline.

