Grade 3 LV SF decreased	pediatric cardiologist

• Cardiac evaluation by Echo but MUGA (Multiple-Gated Acquisition) may be used if clinically indicated

5.4.6.2 QT Prolongation:

Guidelines for the management of prolonged QT interval are as follows: Measure the QT interval (from the start of the Q wave to the end of the T wave) and the preceding RR interval. The corrected QT interval using the Bazett's formula (QTcB interval) will be calculated as the QT interval (msec) divided by the square root of the RR interval (msec). Only the Bazett's formula should be used to calculate the corrected QT interval.

- QTcB interval < 500 msec: No specific therapy needed. Continue pazopanib at the same dose. Serum K⁺, Ca⁺⁺, Mg⁺⁺, and Phos should be monitored and repleted if low (see Section 5.4.4).
- QTcB interval ≥ 500 msec: Hold pazopanib, review concomitant medications, and replete serum K⁺, Ca⁺⁺, Mg⁺⁺, and Phos as needed. The EKG should be repeated within 7 days and if the QTcB interval is < 500 msec then resume pazopanib at a reduced dose. If the QTcB interval remains ≥ 500 msec, the patient must be removed from protocol therapy.
- 5.4.7 Delays in Wound Healing:

Patients treated with VEGF blocking agents appear to have an increased risk of wound healing complications. Therefore, if patients require elective major surgery on study, pazopanib should be held for 14 days prior to surgery and for 14 days after surgery (see Section 3.3.7). Pazopanib should not be restarted if there is evidence of wound healing complications such as a wound infection. Patients who require surgery less than 14 days from treatment with pazopanib should be monitored closely for wound complications. Patients who require major surgery during Cycle 1 of therapy must be removed from protocol therapy.

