The corrected QTcB interval (QTcB) will be listed for each patient and summarized at each scheduled assessment time. Change from baseline will be summarized and an analysis of central tendency (means, medians) will be presented. A categorical analysis for each QTcB parameter will be performed to determine the number of patients at each time point for the following categories:

- QTcB. <450, 450 to <480, 480 to 500, and >500 msec.
- QTcB change from baseline, 30 to <60 msec, and ≥ 60 msec.

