#### **ECG Corrected QT Intervals**

The QTc values based on Bazett's formula is derived by QT interval / ((RR interval/1000)^1/2), where RR interval is in msec.

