#### 9.4.2. ECG Parameters

The following criteria will be used to flag electrocardiogram (ECG) values that are values of potential clinical importance:

To identify QTc (Bazett's) values of potential clinical importance, NCI-CTCAE v4.0 will be used to assign grades (see adverse event 'Electrocardiogram QT corrected interval prolonged'). Note that there is a slight inconsistency between CTCAE v4.0 and ICH E14 (Absolute QTc interval prolongation). It was decided to align with CTCAE for the oncology standard categories.

ECG Parameter	Potential Clinical Importance (PCI) Range	Unit
Absolute QTcB interval	<450	Msec
	≥450 to <480 (Grade 1)	
	≥480 to <500 (Grade 2)	
	≥500 (Grade 3)	
Absolute QTcF interval	<450	Msec
	≥450 to <480 (Grade 1)	
	≥480 to <500 (Grade 2)	
	≥500 (Grade 3)	
Increase from baseline	Increase of $\geq 30$ to $< 60$	Msec
QTcB	Increase of $\geq 60$	

The following criteria will be used to flag other ECG values that are values of potential clinical importance:

ECG Parameter	Potential Clinical Importance (PCI) Range	Unit
PR interval	<110 (L) and >220 (H)	Msec
QRS interval	<75 (L) and >110 (H)	Msec

Normal values per age group for QTcB and QTcF, derived from the 2nd and 98th percentile values in healthy children will be used to identify the values out of normal ranges within each age group.

Age group	0-1 month	1-3 month	3-6 month	6-12 month	1-3 years	3-5 years	5-8 years	8-12 years	12-16 years
QTcB (ms) Boys	413 (378, 448)	419 (396, 458)	422 (391, 453)	411(37 9, 449)	412 (383, 455)	412 (377, 448)	411(37 1, 443)	411(37 3, 440)	407 (362, 449)
QTcB (ms) Girls	420(37 9, 462)	424(38 1, 454)	418 (386, 448)	414(38 1, 446)	417(38 1, 447)	415(38 8, 442)	409 (375, 449)	410 (365, 447)	414(37 0, 457)

Data shown above as median  $(2^{nd} \text{ percentile}, 98^{th} \text{ percentile})$ 

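### SAP 11.8 sorts uncorrected QT by corrected-QT cut-offs, and its QTc-change classes differ from SAP 9.4.2 and the protocol at 30 and 60 msec

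*SAP*

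**What the plan says.** **Shift tables.** The ECG part of SAP 11.8 states: "For each of the QTc and QT intervals, shift tables based on notable parameter categories". The classes are "<450, 450 - <480, 480 - <500" and ≥500 ms, together with a normal range, comparing baseline with the worst post-baseline value.

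**Where the classes come from.** SAP 9.4.2 takes them from the CTCAE term for prolonged corrected QT: "To identify QTc (Bazett's) values of potential clinical importance, NCI-CTCAE v4.0 will be used to assign grades". Its table has rows for QTcB and QTcF and none for uncorrected QT. Its age-specific normal values are likewise announced for the two corrected intervals only. Protocol 9.8.2.6 plans the categorical analysis for QTcB alone.

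**Change from baseline.** SAP 11.8 states: "The changes in QTc values will be categorized into the clinical concern ranges which are specific to changes in QTc: 31-60 and >60 msec". SAP 9.4.2 uses ≥30 to <60 and ≥60 for the QTcB increase, and SAP 11.8 itself points to 9.4.2 for its table of notable ECG values. The protocol has "QTcB change from baseline, 30 to <60 msec" and then ≥60.

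**Top absolute class.** The protocol's bins end with "480 to 500, and >500 msec". SAP 9.4.2 and 11.8 use 480 to <500 and ≥500.

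**The concern.** Uncorrected QT shortens as heart rate rises, and young children have fast heart rates. Cut-offs meant for a rate-corrected interval then measure mainly rate when applied to raw QT. In a fast-hearted child a clearly prolonged QTcB can sit in the lowest QT class; in a slow-hearted adolescent an unremarkable QTcB can sit in a high one. A reader who sees the QT and QTc shift tables side by side, with the same column labels, could take the first as support for the second.

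QT prolongation is a named risk in this protocol, with an eligibility limit on QTcB (3.2.8.4) and a management rule (5.4.6.2), so the ECG tables will be read closely. The change classes raise a smaller problem of the same kind: two definitions of one outcome in one report give counts that need not agree.

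**Working it through.** No stated figure is under challenge, so there is nothing to reproduce first.

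**Inputs**

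- Bazett formula, SAP 9.2.11: "QT interval / ((RR interval/1000)^1/2), where RR interval is in msec".
- Median heart rate and limits of normal by age and sex, SAP 9.4.3. That table stops at 16 years; eligibility runs from 1 to 18 (Protocol 3.2.1).
- Reference value QTcB = 500 ms, the lower edge of the top class in SAP 11.8.

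**Formula.** With RR = 60,000/HR msec, RR/1000 = 60/HR. So QT = QTcB × √(60/HR), and at QTcB 500, QT = 500 × √(60/HR). Raw QT is below 450 when 60/HR < (450/500)² = 0.81, that is, when HR exceeds 60/0.81 = 74.1 bpm.

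**At the SAP's median heart rates**

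| Age (years) | Boys: HR → QT (ms) | Girls: HR → QT (ms) |
|---|---|---|
| 1-3 | 119 → 355 | 128 → 342 |
| 3-5 | 98 → 391 | 101 → 385 |
| 5-8 | 88 → 413 | 89 → 411 |
| 8-12 | 78 → 439 | 80 → 433 |
| 12-16 | 73 → 453 | 76 → 444 |

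Nine of the ten groups fall in the <450 class, including all eight under 12 years. Boys of 12-16 fall in 450 to <480. To reach a raw QT of 500 at the median heart rate, QTcB would have to be 500/√(60/73) = 552 (boys 12-16) to 500/√(60/128) = 730 (girls 1-3).

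**Allowing for spread in heart rate.** The SAP does not say which percentiles its heart-rate limits represent. Assume a split-normal distribution around the median, with the limits at either the 2nd/98th or the 2.5th/97.5th percentiles. The share of children with raw QT <450 at QTcB 500 is then:

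| Age (years) | Boys | Girls |
|---|---|---|
| 1-3 | about 100% | about 100% |
| 3-5 | 98% | 99-100% |
| 5-8 | 84-85% | 94-95% |
| 8-12 | 63-64% | 72-73% |
| 12-16 | 47% | 56% |

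**The other direction.** At 50 bpm, the lower limit of normal at 12-16 years, a QTcB of 440 gives QT = 440 × √(60/50) = 482, in the 480 to <500 class. A QTcB of 440 lies within the SAP 9.4.2 normal range for that age (362-449 boys, 370-457 girls).

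**Change classes, value by value**

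| Rise (msec) | SAP 9.4.2 and Protocol 9.8.2.6 | SAP 11.8 |
|---|---|---|
| 29 | none | none |
| 30 | 30 to <60 | none |
| 31 | 30 to <60 | 31-60 |
| 59 | 30 to <60 | 31-60 |
| 60 | ≥60 | 31-60 |
| 61 | ≥60 | >60 |

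In whole milliseconds only 30 and 60 differ. If derived QTcB is kept unrounded, rises from 30 to just under 31 are also left out by SAP 11.8.

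**The case against.** Four objections deserve weight.

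- **The QT table is not fixed at <450.** A reader might infer from the medians that it can never show prolongation. The SAP's own lower limits of normal refute that. At QTcB 500, raw QT is 548 at 50 bpm (both sexes, 12-16), 522 at 55 (boys 8-12) and 500 at 60 (boys 5-8, girls 8-12), all in the top class. At 12-16 years only about half of children would be in <450, and the SAP gives no heart rates above 16. In the pediatric phase I study the median age was 12.9 years and the four patients with sinus bradycardia were all 12 or older (Protocol 2.4.1), so adolescents may be a large share here. This stands: the fault is sorting by heart rate, not a table frozen at its lowest class.
- **Nothing is hidden.** A reader might infer that a QTcB signal could be missed. SAP 11.8 also requires the QTc shift table, counts of notable values under 9.4.2 (where QTcB ≥500 is Grade 3), a QTc-change summary and ECG listings. A child at QTcB 500 is classed correctly in the QTc table. This stands too.
- **The change classes conflict only at boundaries**, and no decision rule uses them. True, but the report would still carry two definitions of one outcome. The CTCAE-alignment note in SAP 9.4.2 concerns absolute QTc, so it does not explain the difference.
- **The protocol's 480 to 500 bin.** A reader might see a contradiction with Protocol 5.4.6.2: "QTcB interval ≥ 500 msec: Hold pazopanib". The documents do not support that. A reporting bin does not alter a rule applied to an individual ECG, SAP 9.4.2 records a decision to follow CTCAE, and Protocol 9.7.3 allows the RAP to document departures from the protocol's analysis.

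**Conclusion.** The point holds as a minor fault in the planned safety tables. SAP 11.8 gives uncorrected QT a set of classes that the plan defines only for corrected QT. At the SAP's median heart rates, a QTcB of 500 lands in <450 on the QT table in 9 of 10 age-sex groups. That count rests only on the SAP's formula and heart-rate table. The percentages within age groups rest on an assumed heart-rate distribution and are approximate: a clear majority under 12 years, about half at 12-16. The table can err in either direction. It is uninformative as categorised, but it does not conceal a QTcB finding.

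The change classes in SAP 11.8 conflict with SAP 9.4.2 and Protocol 9.8.2.6 at exactly 30 and 60 msec, in whole milliseconds. How many children this affects cannot be known from the documents. Neither matter touches the efficacy analysis, data collection or any clinical rule.

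**What to change.** In SAP 11.8:

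1. Remove uncorrected QT from the categorical shift table. Keep that table for the corrected intervals listed in 9.4.2: QTcB, which is the protocol's measure, and QTcF if it is retained. Name the interval, since 11.8 now says only QTc.
2. Summarise raw QT as a continuous variable by scheduled visit, and keep it in the listings.
3. Use ≥30 to <60 and ≥60 msec for QTc change in every table, as 9.4.2 and the protocol already do.
4. Record in the RAP and the study report that the SAP's ≥500 class replaces the protocol's >500 class. Protocol 9.8.2.6 needs no amendment.

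The cost is a few lines of wording, one categorical table fewer and a small change to the table programs. The data needed are already collected.
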